# 7.2 Primary analysis

Our primary analysis will evaluate the proportion of patients receiving ESPB who require a second parenteral pain medication. This outcome will be compared to external control patients who are selected using propensity score matching at a ratio of 3:1. The propensity score model will include the following variables: age, gender, triage acuity level (ESI score), first ED pain score assessed by nursing, Charlson Comorbidity Index, chronic and initial pain medication type. Data for this outcome will be collected via EHR query as above.

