# 2.10 Sample Size

- This study is a two-stage trial with one planned interim analysis for futility
- Based on the prior 30-month time period (as of May 2022), 572 out of 1071 patients (53.4%) presenting to the ED and meeting the inclusion criteria did not require a 2nd parenteral pain medication during the ED encounter. Thus, we estimate a baseline response rate of 55%.
- Prior work by Nobel et al.¹and Aydin et al.² suggests that no patient will require a second dose of any pain medication after ESPB, but we estimate a conservative response rate of 75% for treatment with ESPB.
- Using Simon's optimal two-stage design with these parameters and  $\alpha$  = 0.05,  $\beta$  = 0.10, we estimate that 18 subjects will be required at the interim analysis and 54 subjects will be required to complete this study.
- Using a Bayesian two-stage design, where interim analysis is planned at one-third total enrollment and a stopping rule if there is only a 10% probability of ESPB demonstrating a 75% response rate, we estimate that 45 total subjects (15 at interim analysis) will be required to achieve a 1.4% chance of stopping early and 95.2% chance of rejecting the null hypothesis.
- This study will aim to achieve a total enrollment of 60 subjects who receive ESPB to account for losses to follow up and withdrawals from the study. Up to 180 (3:1 ratio) historical controls will also be included in the study thus the total enrollment including both treatment and control patients is 240.

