# 7.3 Interim analysis

Both a Simon's optimal two-stage and Bayesian two-stage design were used to estimate sample size (see section 2.10 above) with the Simon's design yielding a slightly larger group for interim analysis (18 patients). Thus, we will plan to perform an interim analysis at 18 recruited patients who have received the ESPB and if 8 or more patients receive a second parenteral pain medication then the study will be ended for futility.

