#### 7.4 Other outcomes

Other outcomes unique to study patients (received ESPB as part of this study) including change in pain score, follow up assessment outcomes, complications, and patient satisfaction will be analyzed before-after the ESPB, change over time, or descriptively as appropriate. Secondary outcomes derived from EHR query (ED operations metrics, opioid medication usage and prescriptions) will be analyzed for study patients in comparison to external controls. All comparisons to external control patients will be made using data collected via EHR query rather than prospectively collected data (investigator collected pain scores, patient satisfaction, follow survey results, etc.) which will be reported descriptively and without comparison to controls.

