#### 8 RISK ASSESSMENT

# 8.1 Potential Risk to Subjects

This study is a single treatment arm trial of ESPB for uncomplicated renal colic to investigate efficacy and complications. Prior studies did not report any major or minor complications as a result of ESPB performed by emergency physicians. However, in prior studies performed perioperatively by anesthesiologists, the following complications were identified: local anesthetic toxicity or allergy, infection or bleeding of the soft tissue overlying the needle insertion site, vascular puncture, pneumothorax, and failed block. Based on prior literature, complications are considered extremely rare because the potential space superficial to the T8 transverse process (site of injection to create plane block) is far from the spinal cord, pleura and major blood vessels. Additional risks to participants include risk of delay in care or other analgesia medication as well as temporary discomfort (lasting less than 1 hour) due to the procedure. Additional risks to both participants and external controls (whose data is secondarily collected from EHR query) are loss of confidentiality.

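### The target, interim and primary analysis count only patients who received the block, so a consented patient given a second parenteral analgesic beforehand who does not proceed goes uncounted, while a control with the same course is a failure

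*Combined protocol and SAP*

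**What the plan says.** Three counts are restricted to patients in whom the block was done.

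- Primary analysis (7.2): "Our primary analysis will evaluate the proportion of patients receiving ESPB who require a second parenteral pain medication". These patients are compared with propensity-matched external controls, three per ESPB patient.
- Interim (7.3): "we will plan to perform an interim analysis at 18 recruited patients who have received the ESPB", with the rule "if 8 or more patients receive a second parenteral pain medication then the study will be ended for futility".
- Target (2.10): "aim to achieve a total enrollment of 60 subjects who receive ESPB". The number is set above the calculated 54 "to account for losses to follow up and withdrawals from the study".

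Section 3.6.1 starts the ESPB outcome after the block. Section 4.7 places written consent before any study procedure. Sections 5.2 and 5.3 then list supplies, positioning, monitoring, collection of the drug from pharmacy, a pain score, a checklist that re-confirms eligibility, and a timeout. Section 8.1 names "risk of delay in care or other analgesia medication" among the risks to participants.

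Participants enter on one parenteral dose (4.2) and controls on at least one (4.4). No section defines a set of all consented patients, or says how to count someone who is given a second drug between consent and block.

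**The concern.** The time between consent and injection acts as a filter on the ESPB group only. For one kind of patient the filter is tied to the outcome by definition. Someone who is given another parenteral analgesic while waiting, and then does not have the block, has had the primary event. That person is outside the 18, outside the 60 and outside the primary analysis, and recruitment continues until enough others have been blocked. A control who needs a second dose just as early stays in and counts as a failure.

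Matching does not repair this. The covariates in 7.2 are demographics, triage acuity, first nursing pain score, comorbidity, and chronic and initial pain medication. None describes what happens after the first dose.

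Two decisions are exposed. The ESPB response rate could look better than it would among all who agreed to treatment, and the futility rule could be less likely to stop an ineffective treatment.

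**Working it through.** **Inputs from the documents.** Null response 55% and target response 75% (2.10); alpha 0.05 and beta 0.10 (2.10); 18 patients at the interim, with a stop at 8 or more failures, which is 10 or fewer responders (7.3); 60 ESPB patients and up to 180 controls (2.10).

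**Reproducing the plan's figure.** An exact binomial search for Simon's optimal design, one-sided 0.05 with 90% power, gives 18 at stage 1 and 54 in total. It continues if more than 10 respond and claims success if more than 35 respond. Exact type I error is 0.0477, power 0.9007, and the chance of stopping early at a 55% response is 0.609. Both 18/54 and the rule in 7.3 are reproduced, so the sample-size arithmetic is not at fault.

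**Assumptions.** Let f be the share of consented patients not blocked and q the share of those who would have needed no second drug. The documents give neither. Assume the block has no effect, so that 55% of all consented patients respond.

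**Formulas.**

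- Observed response among blocked patients: p = (0.55 − f × q) / (1 − f). For example, 0.55 / 0.95 = 57.9%; 0.55 / 0.90 = 61.1%; (0.55 − 0.10 × 0.75) / 0.90 = 0.475 / 0.90 = 52.8%.
- Chance of the futility stop: P(X ≤ 10), with X binomial (18, p).
- Chance of a false claim: exact probability that the trial passes the interim and the pooled z statistic exceeds 1.96 in favour of ESPB, with 60 at p against 180 at 55%. The two groups are treated as independent, ignoring the matching.

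| f | q | Observed ESPB response | Futility stop at 18 | False claim for ESPB |
|---|---|---|---|---|
| 0 | – | 55.0% | 60.9% | 2.0% |
| 5% | 0 | 57.9% | 51.0% | 4.9% |
| 10% | 0 | 61.1% | 39.8% | 11.2% |
| 10% | 27.5% | 58.1% | 50.4% | 5.1% |
| 10% | 55% | 55.0% | 60.9% | 2.0% |
| 10% | 75% | 52.8% | 68.0% | about 1% |

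Without the interim stop, the false-claim rate is 2.4% with nobody removed and 12.7% with 10% removed, all failures. If the final decision used the 54-patient Simon boundary instead, type I error would go from 4.8% to 10.6% (f = 5%, q = 0) or 21.6% (f = 10%, q = 0).

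**How few patients matter.** Take 45/60 (75%) against 99/180 (55%): Fisher p = 0.006. Adding 3 uncounted failures gives 45/63 = 71.4% and p = 0.026. Adding 6 gives 45/66 = 68.2% and p = 0.079.

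**The case against.** A treated population is a defensible choice in a single-arm phase 2 trial whose stated exposure is performance of the block (7.1). The size is also unknown: 10% lost, every one a failure, is a severe case. If those lost respond at half the control rate (27.5%), the false-claim rate is 5.1%, against 2.0% with nobody removed. The direction can reverse. Section 4.2 sets no minimum current pain, so a patient whose first dose takes effect may decline the needle, which removes a responder. All of this stands, and it limits what can be said about size and sign. It does not remove the asymmetry for the patient given a second drug before the block, because that event is itself the primary outcome.

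A reader might go further and infer that a started but abandoned injection is excluded, or that patients who withdraw after the block are dropped from the primary analysis. The documents say neither. They do not define whether a partial injection counts as having received the block. Section 8.1 lists a failed block as a complication, which suggests that a completed but ineffective block stays in. Section 2.10 only enlarges the target for losses and withdrawals; no section removes such patients from the primary analysis.

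The problem overlaps with the choice of outcome start. A patient who is never blocked has no start under 3.6.1, so changing the population without changing the start would not work.

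**Conclusion.** The point holds as a selection problem between consent and block. The plan leaves out consented patients who meet the primary event before the block and do not proceed, and it has no matching exclusion for controls. Bias in favour of ESPB is likely but not certain, and the documents cannot fix its size. If 5% to 10% of consented patients are lost and all are failures, an ineffective block would show 57.9% to 61.1% response instead of 55%. False claims would be 4.9% to 11.2% instead of 2.0%, and the chance of stopping for futility would be 51% to 40% instead of 61%. If those lost are mainly patients whose pain eased, the bias runs against ESPB. If few are lost the effect is small, but the plan as written would not show which case applies.

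It should be corrected before the analysis, because the selection can be tied to the outcome and the remedy is mainly wording.

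**What to change.** - **7.2 and 7.3:** make the primary and interim set every participant who consented and met the eligibility criteria at consent, whether or not the safety screen or the block was completed. Defining the set by passing the safety screen would not be enough. That checklist covers preparation and the eligibility re-check, so patients who leave during preparation would still be lost.
- **Outcome start:** take the outcome from the index-visit EHR and count any parenteral analgesic after the qualifying first dose, with the same start in controls. Align 3.6.1 with this.
- **Supportive analysis:** keep the set who received the block. State whether a started but incomplete injection belongs in it.
- **Reporting:** give the number consented but not blocked, with reasons.
- **2.10:** state that loss to later follow-up does not remove a participant from the primary analysis, because the outcome is complete at the index visit.

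The cost is wording and no extra procedures, since the EHR query is already planned (6.4). The consent pages are not in the copy reviewed, so check that they permit use of index-visit data from participants who are not blocked. If 60 blocked patients remains the recruitment target, 5% or 10% not blocked means 64 or 67 consented (60/0.95 and 60/0.90, rounded up). At three controls each that is 192 or 201, above the 180 in 2.10, so that figure or the ratio would need adjusting. The ESPB response rate may come out slightly less favourable.

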#### 4.2 Inclusion Criteria

- Adult (>18 years) emergency department patient presenting with pain due to uncomplicated urolithiasis
- Imaging confirmation of urolithiasis on the index encounter or prior encounter within 7 days
- Patient received one dose of parenteral pain medication in the ED

Rationale for inclusion criteria: We seek to enroll adult patients who have pain that initially required parenteral medications to treat and thus, may benefit from adjunct therapy to treat severe kidney stone related pain.

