# 4.4 Selection of external control patients

External control patients will be selected from a population of patients meeting the following criteria: 1) adult ED patient with the diagnosis of uncomplicated kidney stones; 2) received at least one dose of parenteral medication while in the ED; 3) presentation to the ED between 7/1/2021 and the study start date. From this population, propensity score matched control patients will be selected at a ratio of 3 controls to 1 ESPB patient. External control population patients are not active patients in this study and analysis of their data will be secondary use of data collected during routine care. To provide valid comparison between control patients and ESPB patients, we will compare pain scores obtained by the treatment team (bedside nurse). For all other primary and secondary outcomes, data collection utilizes EHR query that does not require prospective data collection. Please see the data collection section of this protocol for further details.

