# 4.6 Screening

- Study team members will screen for patients using the ED track board and other patient lists/reports within MiChart (EPIC EHR)
- Study team members will review potential subjects' presenting symptoms, prior medical history, and imaging findings
- Study team members will then notify a physician investigator on call of potential subjects currently in the ED
- Physician investigator will review inclusion and exclusion criteria with other study team members (if they did not perform screening personally) as well as the potential subject

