# **5 STUDY PROCEDURES**

# 5.1 Study Design and Workflow

This study is designed to be a pragmatic, single treatment arm two-stage trial that investigates the efficacy of the ESPB to treat pain related to kidney stones in ED patients in comparison to an external control group. The overall study workflow is diagrammed in Figure 1B and Figure 1C. We plan to have our study team members screen for patients based on the availability of the ED ultrasound team - a clinical care team that performs diagnostic and ultrasound guided procedures at the bedside in the ED. Eligible patients will be approached by a study investigator (the proceduralist) who will obtain informed consent and perform the ESPB. The investigator will also collect data from the patient 1 hour after performing the procedure. Follow up assessments using a web-based survey are an optional sub-study. Participants who do not elect to participate in the optional sub-study will receive a telephone call at day 30 to assess only for adverse events. Study participation will be complete after final follow up assessment.

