# 6.2 Primary data collection during index ED visit

A study team member (coordinator or other investigator) other than the proceduralist performing the ESPB will assess pain prior to and 1 hour after the procedure. Prior history of kidney stones and urologic procedures will be collected. A safety screen will also be performed prior to procedure by the proceduralist. Data entry into REDCap will occur via electronic case reporting form.

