# 6.4 Secondary data collection from the EHR

Variables regarding patient demographics, ED operations metrics, diagnoses, medical history, procedures performed, other healthcare encounters, nurse assessments of pain, medications administered, and prescriptions provided during the index ED visit will be obtained using direct query to the EHR databases (RDW, HSDW, Caboodle, Clarity) and confirmed with manual chart review if needed. Using the same EHR query we will also collect data regarding historical control patients (external controls that did not receive ESPB). Control patient data will be collected as secondary data collection of routinely collected health information.

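### The propensity model in section 7.2 has no stone-history or return-visit variable, so these may stay unbalanced in the primary comparison; both could be added cheaply from the planned EHR query

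*Combined protocol and SAP*

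**What the plan says.** The primary outcome, the share of patients given a second parenteral analgesic, is compared between ESPB patients and external controls matched 3:1. On the matching model, section 7.2 says "The propensity score model will include the following variables: age, gender, triage acuity level (ESI score), first ED pain score assessed by nursing", and the list ends with "Charlson Comorbidity Index, chronic and initial pain medication type". Section 7 states no other adjustment, balance criterion or sensitivity analysis for unmeasured confounding.

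The two groups enter by different routes.

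- **ESPB patients.** Screening covers "presenting symptoms, prior medical history, and imaging findings" (section 4.6). Eligibility asks for "Imaging confirmation of urolithiasis on the index encounter or prior encounter within 7 days" (section 4.2). Staff "screen for patients based on the availability of the ED ultrasound team" (section 5.1).
- **Controls.** Section 4.4 asks for an "adult ED patient with the diagnosis of uncomplicated kidney stones", at least one parenteral dose and a visit within a date window. It states no imaging requirement and no 7-day condition.

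On the data, section 6.2 says of the ESPB group: "Prior history of kidney stones and urologic procedures will be collected". Section 6.4 describes an EHR query, used for both groups, that includes "diagnoses, medical history, procedures performed, other healthcare encounters". Imaging findings are not among the variables it names.

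**The concern.** The comparison is not randomized, so it is only as good as the variables on which the groups are made alike. A factor confounds the comparison if its share differs between the groups after matching and it also predicts a second parenteral dose.

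Return status could do both. A patient imaged at a visit a few days earlier is eligible for ESPB, and nothing in the plan keeps the share of such patients equal among controls. Section 3.1 attributes most initial and repeat ED visits to uncontrolled pain, so a link between return status and a second dose is plausible. Prior stone disease and urologic procedures could act in the same way.

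At stake is whether a difference in second-dose rate can be credited to the block. More returning patients with refractory pain in the ESPB group would hide a benefit; more of them among controls would create one.

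**Working it through.** **1. The plan's own baseline.** Section 2.10: 572 of 1071 had no second dose. 572/1071 = 53.4%, which reproduces the stated figure. The control second-dose rate is therefore 100 − 53.4 = 46.6%.

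**2. Coverage of the model.**

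| Item | Role for ESPB entry | Stated for controls (4.4) | In the 7.2 model | In the 6.4 query |
|---|---|---|---|---|
| Presenting severity | reviewed (4.6) | one or more parenteral doses | in part: pain score, ESI, first drug | yes |
| General medical history | reviewed (4.6) | none | in part: Charlson index, chronic medication | yes |
| Prior stone or urologic procedure | collected (6.2) | none | no | diagnoses, history, procedures |
| Recent visit for the stone | eligible if imaged within 7 days (4.2) | neither required nor excluded | no | other encounters |
| Imaging findings | reviewed (4.6), confirmation required (4.2) | none | no | not named |

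**3. Size of a residual bias.** For one binary factor:

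bias = (difference in its prevalence left after matching) × (difference in second-dose risk with and without it).

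The documents give neither input. Assume a 10-point prevalence difference and a 15- to 30-point risk difference:

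- 0.10 × 0.15 = 1.5 points
- 0.10 × 0.30 = 3.0 points

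The planned effect is 75 − 55 = 20 points.

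**4. Effect on a false finding of benefit.** 60 v 180 patients (section 2.10), two-sided 0.05 assumed because section 7.1 gives alpha without sidedness, no block effect, matching ignored:

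- SE = √[0.466 × 0.534 × (1/60 + 1/180)] = 0.0744
- Chance of a false benefit = 1 − Φ(1.96 − bias/SE)
- No bias: 2.5%
- 1.5 points towards ESPB: 1 − Φ(1.96 − 0.202) = 3.9%
- 3 points towards ESPB: 1 − Φ(1.96 − 0.403) = 6.0%

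**5. Effect on power if the bias runs against ESPB.** Two-proportion comparison, 60 v 180, true ESPB response 75%, observed response lowered by the bias:

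| Control response | No bias | 1.5 points | 3 points |
|---|---|---|---|
| 53.4% (observed) | 86% | 80% | 73% |
| 55% (planning value) | 80% | 73% | 65% |

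**6. Why balance should not be judged by p-values.** For a 0.2 SD imbalance at 60 v 180, the expected test statistic is 0.2/√(1/60 + 1/180) = 1.34. The power to detect it is about 27%, so a test misses it about 73% of the time.

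**The case against.** Four objections deserve an answer.

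**The model is not blind to what screening looks at.** First pain score, ESI and first drug reflect presenting severity; the Charlson index and chronic medication reflect medical history. A reader might infer that the model holds none of the screening items. That is not so: only imaging is wholly absent. But these are general proxies, and two patients alike on all of them can differ in stone history or return status.

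**Selection on stone severity is not documented.** A reader might infer that staff choose patients by how bad the stone looks. Section 4.6 says that staff review symptoms, history and imaging and then notify an investigator, which is also what checking eligibility requires. It refers to general medical history; stone history appears only as data collected under section 6.2. The stated driver of who is screened is ultrasound-team availability. This stands: imbalance is possible, not shown.

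**Controls may be return visits too.** Section 4.4 does not exclude them, so the documents state no difference between the groups. This also stands. The gap is that nothing equalizes the share.

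**Larger biases do not fit the protocol's figures.** A 20-point prevalence gap with a 30-point risk difference gives 6 points and a 12% chance of a false benefit. For return visits this fits poorly with section 3.1, which puts returns at up to one in ten with no 7-day limit. If about 10% of controls are returners and returners need more second doses, the ESPB share can be at most 10 points lower, which caps bias towards ESPB at 10 × 30 = 3 points. A 20-point gap would need about 30% returners among ESPB patients, and that would favor ESPB only if returners needed fewer second doses. The 6-point case is therefore not used here.

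**Conclusion.** The point holds as a cheap improvement to the primary analysis. The section 7.2 model has no stone-specific or return-visit variable, its existing terms cover presenting severity and comorbidity only in part, and the imaging and 7-day conditions stated for ESPB patients are not stated for controls. Stone history and return status may therefore be unbalanced after matching and bias the comparison in either direction.

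The direction and size are unknown. The figures of 1.5 to 3 points, about 4% to 6% for a false benefit, and the matching losses of power are illustrations. They rest on assumed prevalence and risk differences that remain after matching, treat the groups as independent, and use a two-sided 0.05 test. They do not show that the comparison will be biased by that amount. Some residual confounding is inherent in an external-control phase 2 design; this part of it can be reduced with data that the plan already intends to query.

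**What to change.** In section 7.2, add two terms, defined identically in both groups and taken from the section 6.4 query:

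- (a) prior stone diagnosis or urologic procedure;
- (b) ED visit for stone in the previous 7 days.

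State the look-back period for (a). Use the EHR version for both groups, not the history taken prospectively from ESPB patients alone.

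State that balance on all covariates in the matched sample will be judged by standardized mean differences before outcomes are viewed. Section 7.1 does not say that its tests will serve this purpose, and they are too weak for it at this size.

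Keep imaging features such as hydronephrosis or an obstructing stone out of the main model. The query does not name them, and they may be missing more often in one group. Use them only in a sensitivity analysis, if reports are available for both groups.

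Cost: a slightly longer query, two more model terms with about 60 treated patients, and slightly fewer close matches from a pool of about 1071/30 = 36 visits per month. Report review is needed only if the imaging sensitivity analysis is done.

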#### 3.6.2 Secondary Outcomes

- Difference in visual analog scale pain (1-10) from prior to procedure to first pain assessment after 60 minutes from completion of ESPB assessed by bedside nurse
  - Historic data from the U-M ED suggests that the median maximal pain reduction (last pain score minus first) in the ED is a mean reduction of 3.4 points (SD = 3.0) from a starting value of 7.9.
- ED operational quality metrics:
  - o Rate of admission to hospital
  - Rate of 72-hour return to the ED
  - ED length of stay
- Safety outcomes and complications at day 30

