# 5.2 Pre-procedure preparation and safety screen

The proceduralist will explain the ESPB to the patient and answer all questions while obtaining informed consent. After this, the proceduralist and assistants will obtain all nerve block supplies, a department ultrasound system, and properly position the patient. The proceduralist will also ensure that appropriate monitoring equipment (telemetry and pulse oximetry) is in place, primary provider team and primary beside nurse are informed of the procedure, and local anesthetic is obtained from the ED pharmacy. The proceduralist will calculate the maximum safe dose of local anesthetic for the patient. The long-acting local anesthetic to be used in this study is 0.5% Ropivacaine (5 mg/mL) for which the maximum safe dose is 3 mg/kg in 8 hours. The dose will be calculated based on patient weight with a maximum dose of 150 mg (30 mL). Peripheral nerve block is considered on-label use of ropivacaine and the study dose (up to 150 mg) and volume (30 mL) are within the suggested ranges of the approved label. The proceduralist will also confirm the patient does not have allergy to local anesthetic. The proceduralist will also ensure availability of lipid emulsion (Intralipid) in the ED pharmacy. Intralipid is a medication used to treat local anesthetic systemic toxicity (LAST) and would only

be administered in the event of development of LAST. A study team member other than the proceduralist (coordinator or other investigator) will perform a pre-procedure assessment of pain using the visual analog scale. All pre-procedure preparation elements, assessment of pain, and re-confirmation of eligibility criteria will be recorded as the safety screen checklist in the REDCap database.

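### The propensity model adjusts for pain at the start of the visit but for nothing measured after the qualifying dose, leaving a likely confounder of the primary comparison whose sign and size are unknown

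*Combined protocol and SAP*

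**What the plan says.** Section 7.2 defines the primary analysis as the proportion re-dosed after ESPB and states: "This outcome will be compared to external control patients who are selected using propensity score matching at a ratio of 3:1". The full covariate list is "age, gender, triage acuity level (ESI score), first ED pain score assessed by nursing, Charlson Comorbidity Index, chronic and initial pain medication type". The only pain measure in it is the "first ED pain score assessed by nursing".

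The arms enter at different points in the visit:

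- **ESPB.** Section 4.2 requires "Patient received one dose of parenteral pain medication in the ED". The patient is then screened (4.6), consented (4.7) and prepared (5.2), subject to availability of the ultrasound team (5.1). Before the block a study team member "will perform a pre-procedure assessment of pain using the visual analog scale".
- **Controls.** Section 4.4 requires an adult with the diagnosis who "received at least one dose of parenteral medication while in the ED". No index time is set.

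Neither text sets a pain threshold after the first dose. Section 6.4 obtains nurse pain assessments and medications given by EHR query, and uses the same query for controls. Section 7.4 restricts comparisons with controls to EHR data. No sensitivity analysis for unmeasured confounding is described.

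**The concern.** Treated patients pass a selection step after the first dose that controls do not, and no matching variable describes the patient at that step. Initial medication type adjusts for the drug given, not for the response to it. Section 3.6.2 treats the first pain score as the starting value (7.9), so it is a baseline measure.

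The selection could run either way. Patients still in pain may be readier to accept a needle procedure; the ESPB arm would then hold more poor first-dose responders, and a working block would look weaker than it is. Alternatively, patients in severe pain may be re-dosed before a proceduralist arrives and no longer be approached; the ESPB arm would then hold more patients who had already settled, and an inert block could look effective. Without randomisation, the covariate set is the main protection against both, and as written the matched analysis would not show which had occurred.

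**Working it through.** **Inputs from the documents.** Historical response (no second parenteral dose) 572/1071 = 0.534, rounded up to a baseline of 0.55; target response 0.75; Simon α = 0.05, β = 0.10, 18 and 54 patients; 60 ESPB patients and up to 180 controls (all 2.10). Futility stop at 8 or more of 18 re-dosed (7.3). Significance level 0.05 (7.1); its sidedness is not stated and two-sided is assumed for the two-arm test.

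**The plan's own figure.** Exact enumeration of Simon's optimal design gives 10/18 and 35/54, with α = 0.0477 and power 0.9007. This reproduces 18 and 54. Eight or more re-dosed of 18 is the same as 10 or fewer responders, so the stop rule agrees as well.

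**Size of a possible bias.** The splits below are assumptions, not figures from the documents. Let a patient with adequate relief from the first dose respond with probability a and one without with probability b. If the share with adequate relief differs between arms by Δ and the block does nothing, bias = Δ × (a − b).

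Two splits averaging the historical rate, taking half the patients as adequately relieved:

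- 0.5 × 0.75 + 0.5 × 0.318 = 0.534
- 0.5 × 0.85 + 0.5 × 0.218 = 0.534

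Three splits averaging 0.55, with the relieved share set to (0.55 − b)/(a − b): 0.65/0.40, 0.75/0.30 and 0.85/0.20.

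| Split a/b | Δ = 10 points | Δ = 20 points | Δ = 30 points |
|---|---|---|---|
| 0.75/0.318 | 4.3 | 8.6 | 13.0 |
| 0.85/0.218 | 6.3 | 12.6 | 19.0 |
| 0.65/0.40 | 2.5 | 5.0 | 7.5 |
| 0.75/0.30 | 4.5 | 9.0 | 13.5 |
| 0.85/0.20 | 6.5 | 13.0 | 19.5 |

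Each entry can be positive or negative. The two historical splits give about 4 to 6 points at Δ = 10; the weakest split gives 2.5. The three splits at 0.55 give 5 to 13 at Δ = 20.

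**Effect on the two-arm test.** With 60 against 180, d = p1 − p2, pooled null standard error se0 and unpooled se1, the chance of a significant result favouring ESPB is Φ((d − 1.96 se0)/se1). With no bias, power at 0.75 against 0.55 is 0.80. At Δ = 20 points, for splits 0.65/0.40, 0.75/0.30 and 0.85/0.20:

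- If the ESPB arm holds more first-dose responders and the block is inert, the chance of a false result favouring ESPB rises from 0.025 to 0.10, 0.23 and 0.42. For the last, p1 = 0.68, se0 = 0.0735, se1 = 0.0707 and Φ((0.13 − 0.144)/0.0707) = 0.42.
- If it holds fewer and the block truly adds 20 points, power falls from 0.80 to 0.54, 0.32 and 0.15.

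These figures treat the arms as independent and ignore the matching.

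**Effect of dropping controls without a score.** Suppose a post-dose score were required and 20% of re-dosed controls had none because they were re-dosed first (an assumed share). Dropping them gives a control response of 0.534/(0.534 + 0.466 × 0.80) = 0.589; at 30% it is 0.534/(0.534 + 0.466 × 0.70) = 0.621. That is 5 to 9 points against ESPB, so a careless fix could do as much harm as the omission.

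**The case against.** The strongest reply is that nothing in the documents shows the imbalance exists. Selection through consent, or through re-dosing before the block, is a conjecture about practice. The first pain score, triage acuity and initial drug are matched and may carry part of the missing information. Pre-block pain is collected, and 7.1 promises a description of all collected variables, so some of the relevant data would be reported anyway. This stands as a limit on certainty. It does not remove the gap, because describing pre-block pain in one arm does not adjust the comparison.

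Several stronger readings are tempting, and the documents do not support them:

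- **That the bias is about as large as the planned effect.** Nineteen points needs both the strong 0.85/0.218 split and a 30-point imbalance. It is an extreme case.
- **That first-dose response divides the population almost in half, or is the main driver of re-dosing.** The 53.4% is the rate of the outcome itself, not a measure of response to the first dose, and no data on predictors of re-dosing are given.
- **That the first score is documented as preceding the dose's effect.** This follows from its being first and being called a starting value; no timing is stated.
- **That a pain-free patient is certainly eligible.** The text lists no threshold, but the eligibility figure cited in 4.1 is not shown.
- **That the futility rule is distorted and the fix would repair it.** The rule in 7.3 is a single-arm count that no matching covariate can change. It stops with probability 0.61 at a true response of 55% and 0.057 at 75%. To read 0.61 as the chance of abandoning a block that adds 20 points requires an assumed no-block rate of 35%, for which there is no evidence.

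**Conclusion.** The concern holds as a likely unadjusted confounder of the primary comparison. The covariate list in 7.2 contains nothing measured after the qualifying dose, and only the ESPB arm is selected after that dose. The sign and size are unknown. Under the assumed splits, bias of about 4 to 6 points at a 10-point imbalance and 5 to 13 at a 20-point imbalance is material against an effect of 20. These are sensitivity figures, not estimates. A common index time alone would not settle the matter, since patients at the same time after dosing can still differ in pain. Adding a score without a common index time would not settle it either. The change should be made before matching is run.

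**What to change.** Amend 7.2 as follows.

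1. Give each control an index time: a time since first parenteral dose matched to an ESPB patient's dose-to-block time, with the control still in the ED and without a second dose at that time. Count the outcome from the index time (block time for ESPB) in both arms.
2. Add to the propensity model the last nurse-recorded EHR pain score between first dose and index time, defined identically in both arms, and time since first dose. Keep the first ED score. Use nurse scores, not the study team's visual analog scale, in line with 7.4. Pairing the last pre-block score in one arm with the first post-dose score in the other would compare different time points and should be avoided.
3. Do not drop patients because this score is missing. Use a missing indicator or multiple imputation, and report missingness by arm.
4. Report the balance of this score after matching.

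Pre-block pain may be shown beside the interim count, but as description only; it would not correct the futility rule.

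The cost is analysis-plan wording and the times of doses and scores from an EHR query that already covers both arms; 5.3 already has the block time documented in the EHR. The downside is fewer eligible controls and some missing scores. The Simon sample size does not change.
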